#### 2.5.1.5: Clinical Benefit Rate

Clinical benefit includes patients with documented CR, RP or SD for those with measurable disease and CR for with non measurable disease.

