## 2 Methods and Analyses

### 2.1 Analyses Samples

Patients were randomized to the following two treatment arms:

- Arm 1: Palbociclib 100 mg po daily.
- Arm 2: Palbociclib 125 mg po daily 3 out of 4 weeks

The study populations for this analysis will include both the intention to treat (ITT) population and the as treated population.

Analysis of pretreatment characteristics and all efficacy outcomes such as PFS and OS, will be based on the ITT population. The efficacy data set consists of all patients regardless of actual treatment.

Those who received at least one dose of protocol therapy (i.e. the as treated population) will form the basis of the safety analyses. The response analyses will include patients with measurable disease or those with non measurable disease who experience a CR. QOL analyses will include all patients who completed at least one QOL assessment (either baseline or follow-up).

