#### 2.5.1.3 Response Rate

Response will be evaluated in this study using the revised international RECIST Criteria (1.1)

All patients who have received at least one dose of therapy and have their disease re-evaluated will be considered evaluable for response (exceptions will be those who exhibit objective disease progression prior to the end of cycle 1 who will also be considered evaluable). Patients on therapy for at least this period and who meet the other listed criteria will have their response classified as CR, PR, SD and PD. Patients with non measurable disease will only have a best response of either CR or 'Non CR/Non PD'.

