#### 2.5.2.3 Response Rate and Clinical Benefit Rate

Response rates (percentages of CR/PR as best response) will be reported by treated arms for patients evaluable for response.

Clinical benefit rates (percentages of CR/PR/SD as best response) will be reported by treated arms for patients evaluable for response.

Response rates and clinical benefit rates will be compared between two arms using the Cochran-Mantel-Haenszel test adjusting for stratification factors at randomization (Table 16).

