Other condition or circumstance			
Patients who were censored			
Reason Censored			
Still Alive			
Withdrawal of Consent			

*Table 16: Response to Treatment*

	Number of Patients (%)		
	Data set: All treated patients with measurable disease		
	Palbociclib 100mg N = ***	Palbociclib 125mg N = ***	
Response to treatment			
CR	XX (%)	XX (%)	XX (%)
PR			
SD			
PD			

\*Stratification CMH test p-value for response rate:  $(CR+PR)/(CR+PR+SD+PD)$

\*\*Stratification CMH test p-value for clinical benefit rate:  $(CR+PR+SD)/(CR+PR+SD+PD)$

*Table 17: Duration of Response*

	Number of Patients (%)		
	Data set: All patients with CR/PR		
	Palbociclib 100mg N = ***	Palbociclib 125mg N = ***	Stratified p-value from log rank test
Duration of response			
Median	XX	XX	p-value =
Min	XX	XX	-
Max	XX	XX	-
Q1	XX	XX	-
Q3	XX	XX	-

*Table 18: Dose information*

Data set: All treated Patients: Cumulative dose (mg)			
	Number of patients		
	Palbociclib 100mg N = ***	Palbociclib 125mg N = ***	Total N = ***
Median	***	***	***
Min	**	**	**
Max	**	**	**
Q1			
Q3			

Cumulative dose (mg)

n

Mean

Std

Median

Min

Max

Q1

Q3

*Similar tables for*

*Daily dose(mg),*

*Dose intensity (mg/week)*

*Relative dose intensity (percent)*

*Cycle 1 and 2 dose intensity (mg/week)*

*Cycle 1 and 2 relative dose intensity (percent)*

90% or more dose intensity: N and percent

Data set: All treated Patients			
90% or more dose intensity: N and percent	Number of patients		
	Palbociclib 100mg N = ***	Palbociclib 125mg N = ***	Total N = ***
No	***	***	***
Yes	**	**	**

Cycle 1 and 2 90% or more dose intensity: N and percent

Data set: All treated Patients			
Cycle 1 and 2 90% or more dose intensity: N and percent	Number of patients		
	Palbociclib 100mg N = ***	Palbociclib 125mg N = ***	Total N = ***
No	***	***	***
Yes	**	**	**

*Table 19: Dose modifications*

Data set: All treated Patients			
At least one dose modification	Number of patients		
	Palbociclib 100mg N = ***	Palbociclib 125mg N = ***	Total N = ***
Yes	**	**	**
Reason of dose modifications Reason 1 Reason 2 ...			

Data set: All treated Patients			
At least done dose Reduction	Number of patients		
	Palbociclib 100mg N = ***	Palbociclib 125mg N = ***	Total N = ***
Yes	**	**	**
Reason of dose reduction Reason 1 Reason 2 ...			

Data set: All treated Patients			
Patients with dose discontinuation	Number of patients		
	Palbociclib 100mg N = ***	Palbociclib 125mg N = ***	Total N = ***
Yes	**	**	**
Reason of dose discontinuation			

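### The clinical benefit rate gives no credit for controlled non-measurable disease, and the SAP sets it on three incompatible denominators

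*SAP*

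**What the plan says.** The definition in SAP section 2.5.1.5 is: "Clinical benefit includes patients with documented CR, RP or SD for those with measurable disease and CR for with non measurable disease" (RP is evidently a misprint for PR). Section 2.5.1.3 fixes the categories open to the second group: "Patients with non measurable disease will only have a best response of either CR or 'Non CR/Non PD".

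Three places then determine who is in the denominator:

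- **Evaluable patients.** Section 2.5.2.3 says "Clinical benefit rates (percentages of CR/PR/SD as best response) will be reported by treated arms for patients evaluable for response". Section 2.5.1.3 defines that group without any measurability condition: "All patients who have received at least one dose of therapy and have their disease re-evaluated will be considered evaluable for response".
- **Response analysis sample.** Section 2.1 says "The response analyses will include patients with measurable disease or those with non measurable disease who experience a CR".
- **Table 16.** The data set is headed "All treated patients with measurable disease", and the footnote gives the benefit rate as (CR+PR+SD)/(CR+PR+SD+PD). There is no row or term for Non CR/Non PD.

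The rate is also tested: "Response rates and clinical benefit rates will be compared between two arms using the Cochran-Mantel-Haenszel test adjusting for stratification factors at randomization". Section 2.3 sets such comparisons at a two-sided 5% level.

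**The concern.** A patient with measurable disease that neither responds nor progresses is SD and counts as benefit. A patient with non-measurable disease in the corresponding state is Non CR/Non PD and does not. This is a stated rule, not a detail left to the protocol: the SAP creates the category, gives it no credit in the definition and no place in the table.

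The denominators add to the problem. Following section 2.5.2.3, a patient with lasting control of non-measurable disease sits in the denominator as a failure, alongside a patient who progressed at once. Following section 2.1 or Table 16, the same patient is absent. Two analysts working from the same SAP could report different benefit rates and different Cochran-Mantel-Haenszel p-values, each with textual support.

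**Working it through.** **The plan's own figures.** The SAP gives no expected benefit rate and no non-measurable share. Its only sizing figures concern the PFS hazard ratio: exp(±1.645 × √(1/58 + 1/58)) = 1.357 and 0.737, matching the stated 1.36 and 0.74. They do not depend on clinical benefit.

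**Notation.** m = share of evaluable patients with non-measurable disease; c = proportion CR/PR/SD in measurable disease; r and q = proportions CR and Non CR/Non PD in non-measurable disease. All four are assumptions.

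**Formulas.**

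- Evaluable (2.5.1.3 with 2.5.2.3): A = (1−m)c + m·r
- Section 2.1: B = [(1−m)c + m·r] / [(1−m) + m·r]
- Table 16: C = c
- Evaluable, with Non CR/Non PD counted as benefit: D = (1−m)c + m(r+q)

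**Shortfall under A.** D − A = m·q, whatever c and r are. With m = 20-40% and q = 50-80%, this runs from 0.20 × 0.50 = 0.10 to 0.40 × 0.80 = 0.32, or 10 to 32 points.

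**Shift under B.** B − c = m·r(1−c) / [(1−m) + m·r], which is never negative, because the only non-measurable patients admitted are successes.

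**Illustration.** Take c = 70%, r = 3%, q = 67% and PD = 30% in non-measurable disease, so that true control is 70% in both disease types.

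| m | A: evaluable | B: section 2.1 | C: Table 16 | D: Non CR/Non PD counted |
|---|---|---|---|---|
| 10% | 63.3% | 70.1% | 70.0% | 70.0% |
| 25% | 53.2% | 70.3% | 70.0% | 70.0% |
| 40% | 43.2% | 70.6% | 70.0% | 70.0% |

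B and C lie close to D here because control was assumed equal in the two disease types. In general C describes measurable disease only.

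**Sensitivity.** With c from 50% to 80% and r from 0 to 5%, at m = 25%, A is 11 to 20 points below the measurable-disease rate, B moves by less than 1 point, and C does not move. At m = 40% the largest shift under B is 1.6 points (51.6% against 50.0%).

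**A trap in the repair.** Read literally, section 2.5.1.3 gives non-measurable disease no PD category. If Non CR/Non PD were credited and nothing else changed, r + q would equal 1 and every non-measurable patient would count as benefit. At m = 25% and c = 70% the rate would be 0.75 × 0.70 + 0.25 × 1 = 77.5%, against 70.0% in the illustration.

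**The case against.** The strongest reply is that the CR-only rule may be deliberate. Sections 2.1 and 2.5.1.5 match: measurable disease, plus non-measurable disease only with CR. Table 16 is limited to measurable disease. Two of the three places therefore leave Non CR/Non PD patients out rather than failing them, and the SAP never equates that category with SD. The protocol, not seen here, may also define clinical benefit. This stands to the extent that the rule cannot be called a plain slip. It does not remove the conflict: section 2.5.2.3 uses the evaluable population, which keeps these patients as failures; section 2.1 admits patients by their outcome; and Table 16 drops CRs that section 2.5.1.5 counts.

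Stronger readings are tempting, but the document does not support them:

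- A reader might infer that the benefit rate follows the mix of disease types whichever denominator is used, or that it is always understated. Both hold only for the evaluable denominator. Under section 2.1 the shift is small and upward, and under Table 16 it is nil.
- A reader might infer that the arm comparison is biased. Measurability is not a stratification factor (sections 2.3 and 2.4.1.2), so the stratified test does not directly adjust for it, but in a randomized trial any imbalance is a matter of chance. Under the evaluable denominator, a 5-point imbalance with q = 50-80% gives a difference of 0.05 × 0.50 to 0.05 × 0.80, or 2.5 to 4 points. With about 90 per arm, the standard error of a difference near 50% is √(2 × 0.25/90), about 7.5 points. A 10-point imbalance (20% against 30%), on the rates in the illustration, gives 56.6% against 49.9%, a 6.7-point difference with about a 14% chance of an unadjusted p below 0.05.

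**Conclusion.** The point holds in this form. The definition credits non-progression in measurable disease but not in non-measurable disease, and the SAP supplies three denominators that cannot all be followed. Only under the evaluable denominator are controlled non-measurable patients scored as failures; there the loss is m·q, or 10 to 32 points on assumed shares of 20-40% and 50-80%. Under section 2.1 the fault is selection on outcome, with a small upward effect. Under Table 16 the fault is a contradiction with section 2.5.1.5, with no effect of the non-measurable share on the rate. The sizes rest on assumed shares, since the SAP gives none; the contradiction itself rests on the text alone. Clinical benefit is a secondary endpoint, and the PFS estimate, OS and the sample size are untouched. The plan should be corrected, but the trial's main result does not depend on it.

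**What to change.** Use one population, all patients evaluable for response, for the benefit rate in sections 2.1, 2.5.1.5 and 2.5.2.3 and in Table 16. Then:

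1. In section 2.5.1.3, allow PD as a best response for non-measurable disease.
2. In section 2.5.1.5, define clinical benefit as CR, PR or SD in measurable disease, and CR or Non CR/Non PD in non-measurable disease, with any minimum-duration rule applied equally to SD and Non CR/Non PD. Correct RP to PR.
3. In Table 16, change the data set heading (otherwise the new row would be empty), add a Non CR/Non PD row, and include it in the numerator and denominator of the benefit rate.
4. Report the objective response rate on one stated denominator that is not selected on outcome, for example measurable disease only.

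If the sponsor prefers to restrict the benefit rate to measurable disease, say so in all four places, delete the non-measurable clause from section 2.5.1.5, and report non-measurable disease separately.

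The cost is SAP wording and, under the first option, one table row. Section 2.5.1.3 already provides for the Non CR/Non PD category, and progression is already assessed for PFS, so no new data should be needed. The choice should be recorded before benefit rates by arm are examined.

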## 2.3 Analysis Conventions

All comparisons between treatment arms will be carried out using a two-sided test at an alpha level of 5% unless otherwise specified. No formal adjustments will be made for the multiplicity of inferences for the other clinical endpoints.

Baseline stratification factors (excluding centre) that will be used to adjust the analyses where appropriate are listed below:

- Visceral metastases (yes versus no)
- duration of exposure to most recent endocrine therapy prior to randomization (4 groups)
  - duration  $\geq$  6 months versus  $<$  6 months in the advanced/metastatic setting
  - duration  $\geq$  24 months versus  $<$  24 months in the adjuvant setting
- Planned use of Fulvestrant versus Tamoxifen versus Aromatase Inhibitor (AI)

\*Add missing/unknown category whenever appropriate.

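### Clinical benefit counts any stable disease as best response, with no minimum duration, and patients with non-measurable disease enter the rate by three different rules

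*SAP*

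**What the plan says.** Clinical benefit rate is a named secondary objective (SAP section 1.1). The SAP specifies it in three places:

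- Section 2.5.1.5: "Clinical benefit includes patients with documented CR, RP or SD for those with measurable disease and CR for with non measurable disease". RP is evidently a slip for PR.
- Section 2.5.2.3: "Clinical benefit rates (percentages of CR/PR/SD as best response) will be reported by treated arms for patients evaluable for response".
- Table 16 footnote, with the outer brackets left off: "CR+PR+SD)/(CR+PR+SD+PD".

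None of the three gives a minimum duration of SD or points to one elsewhere. The only time condition near the response categories is in section 2.5.1.3: "Patients on therapy for at least this period and who meet the other listed criteria will have their response classified as CR, PR, SD and" (progression completes the list). The length of that period is not given.

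The SAP describes the analysis set in more than one way. Section 2.1 says: "The response analyses will include patients with measurable disease or those with non measurable disease who experience a CR". Section 2.5.2.3 uses patients evaluable for response. Section 2.5.1.3 defines these as treated patients whose disease was re-evaluated, plus early progressors, and it allows those with non-measurable disease a best response of CR or Non CR/Non PD only. The heading of Table 16 restricts the data set to treated patients with measurable disease.

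The rate is tested between arms: "Response rates and clinical benefit rates will be compared between two arms using the Cochran-Mantel-Haenszel test", with stratification factors as adjustment. Section 2.3 sets the level: "All comparisons between treatment arms will be carried out using a two-sided test at an alpha level of 5% unless otherwise specified".

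**The concern.** A clinical benefit rate is normally read as a statement about lasting disease control. As written, one scan without progression is enough to be counted. The SAP reports duration of SD nowhere else, since section 2.5.1.4 and Table 17 cover only patients with CR or PR. A reader of the final report could not tell brief from lasting stability.

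The second problem is who is in the rate. A patient with non-measurable disease whose best response is Non CR/Non PD is a failure in one section and absent in others. Section 2.1 admits such patients only if they reach CR, so entry to the denominator depends on the outcome being measured. Two programmers following the SAP could produce different rates from the same data.

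**Working it through.** **1. The plan's own figures.** The SAP gives no assumed rate, sample size or power for clinical benefit. Its figures in section 1.2 concern PFS, and they reproduce.
- Confidence limits with 58 events per arm: exp(±1.645 × √(1/58 + 1/58)) = 1.357 and 0.737, against the stated 1.36 and 0.74.
- Sample size: with λ = ln 2/10 per month, 12 months' accrual and 12 months' follow-up, the event probability is 1 − (e^(−12λ) − e^(−24λ))/(12λ) = 0.704. Then 58/0.704 = 82.3, and 82.3/0.90 = 91.5 per arm, against about 90 stated.

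The exponential model with a 10-month median is therefore a fair stand-in for the SAP's planning.

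**2. What the Table 16 formula measures.** (CR+PR+SD)/(CR+PR+SD+PD) = 1 − PD/(CR+PR+SD+PD). This is exact on the Table 16 set, and also on the section 2.1 set, because neither contains Non CR/Non PD patients.

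**3. How much stable disease would be short-lived.** S(t) = exp(−ln 2 × t/10), with t in months = weeks × 7/30.4375. The SAP does not state when the first re-evaluation takes place, so 4, 8 and 12 weeks are assumed. The 24-week mark is illustrative, and S(24 weeks) = 68.2%.

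| First re-evaluation (assumed) | Progression-free then | Of these, progressed or dead before 24 weeks |
|---|---|---|
| 4 weeks | 93.8% | 1 − 68.2/93.8 = 27.3% |
| 8 weeks | 88.0% | 1 − 68.2/88.0 = 22.5% |
| 12 weeks | 82.6% | 1 − 68.2/82.6 = 17.4% |

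**4. Sensitivity to a difference between arms.** The second arm is S(t)^HR. Power is for a two-sided 5% two-proportion test with normal approximation and pooled variance under the null, as an unstratified stand-in for the CMH test. The hazard ratios are illustrative.

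| Time point | HR 1.36: rates | Difference (points) | Power, 90 per arm | Power, 60 per arm (assumed evaluable) | HR 2.0: power, 90 per arm |
|---|---|---|---|---|---|
| 4 weeks | 93.8% v 91.7% | 2.1 | 8% | 7% | 27% |
| 8 weeks | 88.0% v 84.1% | 3.9 | 12% | 9% | 46% |
| 12 weeks | 82.6% v 77.1% | 5.5 | 15% | 11% | 61% |
| 24 weeks | 68.2% v 59.4% | 8.8 | 23% | 17% | 84% |

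**5. The populations side by side.** For a treated, re-evaluated patient with non-measurable disease and best response Non CR/Non PD:

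| Source | In the denominator? | Counted as |
|---|---|---|
| 2.5.1.3 with 2.5.1.5 and 2.5.2.3 | yes | no benefit |
| 2.1 | no (enters only with a CR) | excluded |
| Table 16 heading | no (measurable disease only) | excluded |

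Table 16 also leaves no place for the non-measurable CRs that section 2.5.1.5 counts.

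To gauge the size, take the 8-week rate of 88.0% and suppose that a share q of evaluable patients has non-measurable disease and none of them reaches CR (q is an assumption). With those patients in the denominator the rate is (1 − q) × 88.0%: 79.2% for q = 10%, 70.4% for 20%, 61.6% for 30% and 52.8% for 40%. With them excluded it stays at 88.0%. The choice of set therefore moves the rate by 8.8 to 35.2 points.

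**The case against.** **The three statements agree, and the protocol may set an interval.** All three specifications count SD as best response, so the SAP does not contradict itself on duration. Section 2.5.1.3 applies RECIST 1.1 and mentions a period on therapy and other listed criteria, which suggests text carried over from elsewhere. The protocol, not shown, may hold a minimum interval. This stands as a limit: it cannot be said that the trial has none. But the SAP's formula neither states nor refers to one, and at most its wording means the end of cycle 1 or the first re-evaluation. If the protocol sets a longer interval, Table 16 as written departs from it.

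**A reader might infer that the rate is exactly one minus the PD share and also that Non CR/Non PD patients are scored as failures.** Both cannot hold at once. The identity needs a set that excludes those patients; scoring them as failures needs the evaluable set, where the identity breaks. What the documents show is an unreconciled denominator.

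**A reader might infer that the CMH test is worthless and that a duration rule would rescue it.** The documents support neither. In section 1.2, 1.36 is the ratio of the upper 90% confidence limit to the estimated hazard ratio, not an effect size, and the same 10-month median is assumed in both arms. The trial is sized to estimate a PFS hazard ratio, not to test. At a hazard ratio of 1.36 power stays low under either definition; only a large effect such as 2.0 shows a material gain. A rate of non-progression is still interpretable if it is labelled as that.

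**Changing the definition late is awkward.** The SAP is dated 2018-08-08, after the clinical cut-off of April 16, 2018 in section 1.4. This also stands: a threshold should come from the protocol, not be chosen now.

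**Conclusion.** The point holds in two parts. First, the SAP as written counts stable disease of any length as clinical benefit. On the measurable-disease set the rate then says only how many patients did not have progression as best response, and it carries no information on durable control. Roughly one in six to one in four of those progression-free at first re-evaluation (17% to 27%) would have progressed or died before 24 weeks. Second, non-measurable disease is handled in three incompatible ways, one of which conditions entry on achieving CR.

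The duration figures rest on exponential PFS with the SAP's 10-month median, a first re-evaluation at 4 to 12 weeks, the illustrative 24-week mark, and all-patient PFS (deaths included) as a proxy for best response in the evaluable subset. The size of the denominator effect depends on the unknown share with non-measurable disease. The inconsistency itself depends on no assumption. This is a weakness of a secondary endpoint and does not touch the primary PFS estimate. It should be corrected for interpretability, not for power.

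**What to change.** 1. In sections 2.5.1.5 and 2.5.2.3 and in the Table 16 footnote, require SD to last at least the minimum interval set in the protocol, measured from randomization, and cite the protocol section. Count patients censored before that point as no benefit. Correct RP to PR.
2. Report the any-SD rate (CR, PR or SD as best response) separately, labelled as disease control.
3. Use one response population in section 2.1, section 2.5.1.3, section 2.5.2.3 and the Table 16 heading, defined without reference to achieving CR. If patients with non-measurable disease stay in the clinical benefit analysis, apply the same duration rule to Non CR/Non PD and add that category to Table 16. If they do not, delete the non-measurable clause from section 2.5.1.5.
4. If the protocol sets no interval, say so, keep the any-SD rate under the disease control label, and mark any duration-based rate as chosen after the clinical cut-off.

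The cost is SAP wording, one more derived variable from assessment dates already needed for PFS (section 2.5.1.1), and a revised analysis set. The reported clinical benefit rate will be lower. No new data are needed.

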### 2.5.2 Analysis of Key Parameters

All efficacy analyses will be presented by treatment arm. The CONSORT diagram will be included.

